#### Inclusion criteria

- 1) Married or considers themselves married
- 2) Living with partner most of the time
- 3) Living within the selected villages in the last 3 months
- 4) Age 18 (or an emancipated minor) to 40 for women; age 18 to 50 for men
- 5) Luganda speaking
- 6) Not currently pregnant
- 7) Has no knowledge of infertility
- 8) Wanting to avoid pregnancy for at least a year (at least one person in the couple)
- 9) Not using a method of contraception at the moment OR only using low-efficacy or ineffective method of contraception (defined as using condom less than 100% of the time, Fertility-Awareness Based methods e.g., counting method, withdrawal method, spermicide, emergency contraception, and sponge)
- 10) Never used a non-reversible method (male or female sterilization)
- 11) Has sex in the past 3 months (woman)

## Recruitment & Sampling

In each village, members of the Village Health Team (VHT) will assist our research staff in identifying potentially eligible couples. For the couples that we attempt to recruit based on the VHT's referral, the VHT will first independently visit couples' homes to introduce them to the study, and gain permission to return with the research assistant. If permission is granted, the VHT will accompany our research assistant to couples' homes to introduce our research assistant.

If both partners are together during this initial meeting, the research assistant will inform them of the overall study together, but will screen and assess eligibility separately, ensuring that participants are able to answer the eligibility screening questions about fertility preferences and current use of contraceptives in a private setting to ensure confidentiality. Research assistants will be trained in to try to separate spouses in a culturally appropriate and sensitive manner. In cases where the research assistant feels separate screening will not be possible, s/he will attempt to reschedule to come back and conduct the screenings separately. If a reschedule is not possible and screening must happen together, the research assistant will conduct a follow-up phone call or house visit with just the woman to confirm the accuracy of her responses. The research assistant will then obtain written informed consent from the participants. See recruitment script for eligibility screening questions. No identifying information will be collected for eligibility screening. The interviewer will proceed to conduct the baseline questionnaire after obtaining written informed consent for both partners.

If only one partner is present during the initial meeting, the research assistant will proceed with the eligibility screening. If the partner (male or female) is found eligible and interested, the research assistant will ask him/her to refer their partner to the study (either by calling their partner themselves, having the partner call the research assistant or the VHT). The research assistant will conduct the eligibility screening with the second partner over the phone, or will return to the house at the scheduled date and time, and follow the same procedures described above to assess eligibility, obtain informed consent for study participation, and conduct the baseline questionnaire.

If an eligible participant is interested, but their partner declines participation, we will provide a referral to family planning services for a nearby clinic to the interested participant (in both the intervention and control villages to maintain balance between the study arms).

Enrolled couples can also refer other couples to the study (snowball sampling). They will provide the study contact to the referred couples directly, who can choose to contact the study team.

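### The last-resort joint screening step checks the woman's answers privately afterwards, which protects their accuracy but not their confidentiality, and gives the man no private check

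*Combined protocol and SAP*

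**What the plan says.** Under Recruitment & Sampling, when both partners are at home the research assistant is to "screen and assess eligibility separately, ensuring that participants are able to answer the eligibility screening questions about fertility preferences and current use of contraceptives". The setting and the reason are given as "in a private setting to ensure confidentiality". Staff are trained to separate spouses tactfully. Where that looks impossible, "s/he will attempt to reschedule to come back and conduct the screenings separately". If this also fails, the last resort applies: "If a reschedule is not possible and screening must happen together, the research assistant will conduct a follow-up phone call or house visit". The target and purpose of that contact are stated as "with just the woman to confirm the accuracy of her responses". Written consent comes next. The section refers to a recruitment script for the questions themselves; the script is not part of the document.

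Two of the Inclusion criteria make privacy important. Criterion 8 is "Wanting to avoid pregnancy for at least a year (at least one person in the couple", so the partners may differ. Criterion 9 opens with "Not using a method of contraception at the moment" and otherwise admits only low-efficacy or ineffective methods.

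The section on pregnancy test procedures sets a different rule for the baseline questionnaire: each partner must have full privacy, and otherwise the interview moves to another time. It has no joint option.

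**The concern.** The plan separates the partners for the sake of confidentiality, yet its fallback aims only at accuracy. As written, a joint screen may include the contraception and fertility questions, and the private contact comes after they have been asked. A woman with something to keep private must then choose, before she has consented to anything, between saying it in front of her partner and answering falsely until staff reach her alone.

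Participant protection is the main thing at stake. The plan itself treats partner conflict as a possible unintended effect: it is the example given under Process Data, and partner violence has its own monitoring section. A lesser issue is that one eligibility answer, the man's on criterion 8, may be given with his wife present and never checked in private.

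**Working it through.** No arithmetic applies, and the plan gives no figure to reproduce. The check sets the relevant sections side by side.

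**Step 1: order of events (Recruitment & Sampling).** (a) Try to screen separately. (b) Try to reschedule. (c) Screen together. (d) Contact the woman alone. (e) Obtain written consent. Step (d) precedes consent, so it can still change who is enrolled. It follows (c), so it cannot change what the partner has heard.

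**Step 2: a woman with something private, taken through (c) and (d).** Assume that she answers truthfully when alone.

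| Situation | Answer at (c) | Partner learns at (c)? | Her answer after (d) |
|---|---|---|---|
| Covert use of an effective method (criterion 9) | Truthful | Yes | User |
| Same | Denies use | No | User, corrected |
| Wish to avoid pregnancy that he does not share (criterion 8) | Truthful | Yes | Wants to avoid |
| Same | Guarded | No | Wants to avoid, corrected |

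The last column does not depend on what she said at (c). Her final eligibility answer is the one she would give if (d) were the first time she was asked. For her, joint questioning on these items adds exposure and no eligibility information.

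**Step 3: the man.** Criterion 8 needs only one partner. If the woman's checked answer is that she wants to avoid pregnancy, the criterion is met whatever he said. If it is not, eligibility rests on his answer from the joint session, and the fallback provides no private contact to check it.

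**Step 4: comparison with baseline.** Screening and the baseline questionnaire both cover family planning. Baseline without privacy is postponed; screening without privacy may go ahead jointly once rescheduling has failed. The section on monitoring intimate partner violence says that violence history is collected at baseline, so the weaker rule applies before staff have that information. A couple screened out never reaches that assessment.

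**Step 5: feasibility of another order.** The fallback already commits staff to reaching the woman alone. The same section already allows a second partner to be screened by telephone when only one is at home. Both routes needed to avoid joint questioning on sensitive items are therefore already in use.

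**The case against.** Much of the case on the other side stands, and it limits the point.

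- **The step is a last resort.** Separate screening is the default, staff are trained for it, and rescheduling must fail first. Only some of the couples who reach the fallback have anything to conceal. The documents support no percentage, and any figure would be a guess.
- **A reader might infer that every joint screen discloses something.** It does not. A guarded answer reveals nothing, and the accuracy check seems to anticipate such answers. What remains is a risk of disclosure, and questioning without privacy.
- **A reader might infer that enrolment rests on unreliable answers.** For the woman the text does not support this: her answers are checked alone before consent. The gap is confined to the man.
- **A reader might infer that a changed decision would alert the partner.** The plan does not say that eligibility is announced at the joint session, or that reasons are given.
- **A reader might infer that these are the women at highest risk, or that conflict is the plan's principal harm.** Neither is documented. The violence-monitoring section expects a low risk, concerns the intervention, and says nothing about which couples cannot be separated.
- **The recruitment script might already defer the sensitive items.** This cannot be excluded. If it does, the protocol text should say so.
- **Recruitment looks finished.** The Data Analysis Plan is in the past tense, and the note on assessment times speaks of travel restrictions during the study. New wording may then help only later use of the procedure.

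None of this answers the remaining point: the fallback serves accuracy only, and is looser than both its own stated aim and the baseline rule.

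**Conclusion.** The point holds as a narrow inconsistency in participant protection. The fallback does not secure the confidentiality for which separate screening was introduced, and it leaves the man's answers without a private check. It affects only couples who reach the last-resort step, a number that the documents do not give and that is presumably small. It has no bearing on sample size, power or the analysis model.

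The conclusion rests on two assumptions: that the unseen script does not already hold back the sensitive items, and that a woman reached alone answers truthfully. The second also underlies the plan's own accuracy check. The change is worth making because it is cheap.

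**What to change.** Reword the fallback in Recruitment & Sampling, and the script to match:

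1. When partners can be neither separated nor rescheduled, ask only criteria 1 to 5 together (marriage, cohabitation, residence, age, language).
2. Ask the woman criteria 6 to 11 (pregnancy, infertility, wish to avoid pregnancy, contraceptive use, sterilization, recent sex) for the first time in the private call or visit already planned.
3. Ask the man separately those of criteria 6 to 11 that apply to him, for example by the telephone route already used for a second partner.
4. Give any ineligibility decision without a reason.

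The cost is protocol and script wording, one short extra contact with the man that the fallback does not now contain, and a slightly later eligibility decision for these couples.

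If recruitment is complete, report how many couples were screened jointly and how many of the women's answers changed at the private check. State also whether the script deferred the sensitive items, and correct the text before the procedure is used again.

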#### Data collection

#### Questionnaires

**Baseline.** After the informed consent process in a one-on-one interview, using a computerized structured questionnaire in the participant's home or another agreed upon location, the Research Assistants will collect demographic information and the measures to assess family planning determinants. Participants can also complete the baseline interview over the phone shortly after enrollment if needed. Total duration ~45 minutes.

- **~7-month assessment**. Research Assistants will conduct a ~7-month follow up with the interviewers using an individual structured interviewer-administered computer-based interview (~45 minutes duration) in the participant's home, another agreed upon location, or via telephone. The 7-month questionnaire will serve as a measure of intervention effects on contraceptive use and relevant determinants of family planning. Total duration ~45 minutes.
- **~10-month assessment**. At ~10-month follow-up the interviewers will conduct an individual structured computer-based interview (~45 minutes duration) in the participant's home or another agreed upon location. Men and women may complete this survey via telephone; however, women must complete a second pregnancy test in-person. The 10-month questionnaire will serve as a measure of intervention effects on contraceptive use, contraceptive continuation, and relevant determinants of family planning. Total duration ~45 minutes (55 minutes for women taking pregnancy test)

\*Note: The study protocol originally planned for 3 and 6-month follow-up time points, but the assessment points were extended due to COVID-19 travel restrictions that occurred during the study.

#### **Process Data**

Brief interviews with participants after each session. After each intervention and control session, all couples will complete a brief semi-structured interview (~5 min) to assess acceptability of the intervention content and structure, rating perceived importance and satisfaction with intervention content, and an open-ended question on what they liked and disliked. These brief semi-structured interviews will also include questions to assess any unanticipated negative adverse events occurring because of the intervention (e.g., partner conflict).

**Exit interviews with participants post-intervention**. Within 3-4 weeks of the pilot intervention, brief semi-structured exit interviews (~15 min) will be conducted with intervention participants (n=70), as well with facilitators (n=2), participating health workers (n=2), and community leaders (n~2-4) to further assess acceptability, feasibility, appropriateness, barriers to implementation/utilization, areas for improvement, and progress on "Family/Community Action Plans." Exit interviews can be conducted in-person or over the phone. See Table 3 for more detail on measures of acceptability and feasibility for intervention content and structure.

**Data collection to assess intervention fidelity.** Facilitators will follow a fidelity checklist to ensure all steps are completed, which will also be monitored in early dialogues and then randomly throughout the course of the study through direct observation of intervention sessions by research

staff to allow for immediate feedback. Staff will complete a session checklist on activities conducted, number of participants, engagement, and issues encountered including those related to community leader participation (providing immediate feedback to ensure fidelity). In addition, a randomly selected portion (~20%) of the dialogues will be audio recorded, transcribed, and analyzed for fidelity.

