## Monitoring Intimate Partner Violence (IPV)

Though we expect the risk of adverse events resulting from participation in the intervention to be low, since we are working with couples and facilitating discussions around sensitive topics, such as family planning and gender norms, we have developed procedures to closely monitor participants in the couples' intervention. The implementation of these procedures will ensure any unanticipated adverse events related to violence or relationship conflict are identified and addressed immediately. First, our baseline data will assess participants' history of experiencing and perpetrating intimate partner violence. We will use this data to identify couples who report a history of violence, so that intervention facilitators can closely monitor those couples, and pay special attention to issues of violence in the intervention sessions to minimize the risk of conflict arising between couples. In addition, after each couples' session, men and women will separately complete a brief questionnaire to collect process data on the feasibility and acceptability of the intervention. In addition to questions on feasibility and acceptability, this questionnaire will include questions to assess if the intervention had any negative consequences on couples' relationships, either during the intervention itself, or since the last intervention session, whether at home or elsewhere. Items will include a modified 3-item version of the Conflict Tactics Scale to assess experience of emotional, physical, and sexual conflict since the last intervention session. Participants will be asked about the frequency of being the recipient of each type of conflict by their partner, as well as the perpetrator of each type of conflict. The questionnaire will also include an open-ended question to probe further on the occurrence of abuse if any is reported. The responses to this questionnaire will be reviewed immediately by the intervention facilitators, as well as a research assistant. Any indication of potential abuse or conflict resulting from the intervention, whether verbal or physical, will be reported immediately to the Investigators, and follow the plan for reporting adverse events (described below) and a protocol to minimize the risk of future adverse events, determine the safety of the participants' continued participation in the study, and refer the couple to support services (see "Protection of Human Subjects" section) for more details.

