## Discontinuation/withdrawal of participants from intervention

In this study, each participant has the right to withdraw from the trial at any time. In addition, the Investigator may discontinue a participant from the trial at any time if the Investigator considers it necessary for reasons such as; an adverse event that requires discontinuation of the intervention or results in inability to continue to comply with study procedures. The reason for withdrawal will be recorded in the Procedures for Recording Adverse Events (CRF).

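### Structured partner-conflict and adverse-event questions are stated only after sessions, so couples who stop attending have no stated route to being asked and harm may be under-reported

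*Combined protocol and SAP*

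**What the plan says.** Under Process Data, a short interview follows every session in both arms: "After each intervention and control session, all couples will complete a brief semi-structured interview (~5 min) to assess acceptability". It is also a harm instrument: "These brief semi-structured interviews will also include questions to assess any unanticipated negative adverse events occurring because of the intervention", with partner conflict given as the example.

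Under Monitoring Intimate Partner Violence (IPV), after each couples' session "men and women will separately complete a brief questionnaire to collect process data on the feasibility and acceptability of the intervention". That form also asks about negative effects on the relationship and includes a modified 3-item Conflict Tactics Scale "to assess experience of emotional, physical, and sexual conflict since the last intervention session". Any sign of abuse or conflict resulting from the intervention goes at once to the investigators, followed by a safety determination and referral to support services. The section says these procedures will ensure that such events are found and dealt with without delay.

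Three other contacts are described:
- **Exit interviews** (Process Data): "brief semi-structured exit interviews (~15 min) will be conducted with intervention participants (n=70"), within 3-4 weeks of the intervention, "to further assess acceptability, feasibility, appropriateness, barriers to implementation/utilization, areas for improvement" and progress on action plans. "Exit interviews can be conducted in-person or over the phone".
- **7- and 10-month questionnaires** (Questionnaires): their stated purpose is contraceptive use, continuation (10 months) and family-planning determinants.
- **Withdrawal** (Discontinuation/withdrawal): "each participant has the right to withdraw from the trial at any time", and the reason is recorded on adverse-event paperwork.

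The Data Analysis Plan does not say how adverse events or acceptability are summarised, or over which denominator.

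**The concern.** Both instruments that ask actively about conflict depend on a session taking place with the couple present, and the conflict scale looks back to the previous session. Conflict at home after one session is therefore picked up only at the next. If that conflict is why the couple does not return, the event and the missing data have the same cause.

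Two things are at stake. First, the harm results of this pilot may describe mainly the couples who kept coming. If conflict makes stopping more likely, the reported rate is too low. Second, the reporting and referral pathway in the IPV section is described as starting mainly from reviewed questionnaire responses, and couples who have left do not complete that questionnaire. The DSMB reports and the investigators' monthly reviews likewise depend on what has been collected.

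**Working it through.** The plan gives no attendance rate, dropout rate or expected harm rate, so there is no figure to reproduce. The check sets each route by which a harm could be learned beside its trigger and stated content.

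| Route | Trigger | Arm | Harm questions stated? |
|---|---|---|---|
| Post-session interview | A session | Both | Yes |
| Post-session questionnaire with conflict scale | A couples' session | Described for the couples' intervention | Yes |
| Exit interview | Within 3-4 weeks of the intervention; no attendance condition | Intervention only | Not among listed topics |
| 7- and 10-month interviews | Calendar time | Not restricted by arm | Not in stated purpose |
| Withdrawal reason | Formal withdrawal | Not restricted by arm | A reason, not the scale |
| Session checklist | A session | Not specified | Participant numbers and issues; no follow-up of absentees stated |

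**Couple A** attends session 1, has conflict at home afterwards and does not return.
1. The form after session 1 is completed before the conflict.
2. The form after session 2, whose recall window would cover it, is not given to them.
3. An intervention couple may be reached at the exit interview, but conflict is not a listed topic. A control couple has no exit interview.
4. A withdrawal reason exists only if the couple formally withdraws. A couple that simply stops coming generates none.
5. The 7- and 10-month interviews may reach them, but no conflict item is stated there.

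**Couple B** attends every session and has conflict after the last one. There is no later session, so the same gap applies.

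**Illustration of size.** The only input from the documents is 70 intervention participants. The rest is assumed: a share d not asked of 10%, 20% or 30%; 5% reporting conflict among those asked; and a true rate h of 5% to 20% among those not asked.

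Full rate = 0.05 × (1 − d) + h × d. At h = 5% this is 5% for every d. At h = 20%:
- d = 10%: 0.045 + 0.020 = 6.5%
- d = 20%: 0.040 + 0.040 = 8.0%
- d = 30%: 0.035 + 0.060 = 9.5%

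If no conflict at all is reported, the one-sided 95% upper limit is 1 − 0.05^(1/n), treating participants as independent:
- n = 70 (all asked): 4.2%
- n = 63 (d = 10%): 4.6%
- n = 56 (d = 20%): 5.2%
- n = 49 (d = 30%): 5.9%

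The loss of precision is small. The larger difficulty is that these limits describe only those asked and say nothing about the rest. Partners' answers are also related, so the limits are somewhat optimistic.

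**The case against.** The strongest case against the point has four parts.

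**Unseen item lists.** The Questionnaires section states purposes, not items. Its baseline description does not mention violence, yet the IPV section shows that baseline measures it. The follow-up questionnaires may therefore contain conflict items too. Table 3 and the Protection of Human Subjects section are cited but cannot be read here. This stands as a limit on wording: the finding is that no route is stated, not that none exists. Even if the items are there, a 7-month interview would not meet the aim of acting without delay.

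**Other channels.** The withdrawal reason goes on adverse-event paperwork, the investigators log and review all events monthly, and the reporting duty for conflict is not expressly limited to the post-session form. A reader might infer that the safety pathway cannot start for couples who leave. The documents do not support that: it can start if someone learns of the event. But these channels are passive, and a recorded reason is not a private question put to each partner.

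**Acceptability.** A reader might infer that acceptability, too, is measured only among attenders and is therefore overstated. The documents do not support this. The exit interviews also assess acceptability, can be done by phone and carry no attendance condition. If 70 is the whole intervention arm, they are meant to cover those who stopped. What stands is narrower: the plan does not say whether 70 includes non-attenders and withdrawals, and control couples have no exit interview.

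**Comparison between arms.** A reader might also infer a biased between-arm process comparison. The Data Analysis Plan specifies none, and control-session content is not described, so differential dropout would be conjecture.

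It is also fair to say that contacting people who have left, possibly because of violence, raises consent and privacy questions. That shapes the fix but does not close the gap.

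**Conclusion.** The point holds for harm. As written, active questions about conflict and adverse events are tied to sessions. Couples in either arm who stop attending, and any couple after its last attended session, have no stated route to being asked. The undertaking in the IPV section is not met for them, and reported conflict may be understated.

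The direction of bias rests on the assumption that conflict makes stopping more likely, which is plausible but not shown in the documents. The size is unknown. The range shown, from no change to a rise from 5% to 9.5%, follows from assumed inputs and is not an estimate for this trial. For acceptability, what remains is to clarify who is interviewed and to report the denominator.

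**What to change.** In Process Data and the IPV section, state that:
1. The existing brief conflict and adverse-event items are also put, privately and separately, to each partner of any enrolled couple that stops attending, in both arms, unless that person refuses or has withdrawn consent to contact.
2. The same items are asked at the exit interview and at the 7- and 10-month interviews, whatever the attendance. The follow-up interviews matter most for control couples, who have no exit interview. If the follow-up questionnaires already contain these items, say so.
3. Any report of conflict enters the existing IPV reporting and referral pathway.
4. Exit interviews include intervention participants who stopped attending.

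In the Data Analysis Plan, report conflict and acceptability with all enrolled couples as the denominator, give the number not asked, and show those who stopped separately.

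The cost is a few extra contacts using a roughly 5-minute instrument and existing staff, plus a few items added to interviews already planned. Response will be incomplete, and the privacy safeguards already used for interviews must apply, especially by phone. The Data Analysis Plan is written in the past tense. If collection is finished, the denominators can still be reported and the limitation stated.
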